8.6.3 Utility

- User acceptance of the ARGOS-SC system at the investigational site by means of evaluation of physician acceptance questionnaires by investigators (18 items) at V09 (month 12) and V13 (month 36). All these parameters will be analysed using a frequency table.
- User acceptance of the ARGOS-SC system at home by means of evaluation of patient acceptance questionnaires by patients (16 items) at V09 (month 12) and V13 (month 36). All these parameters will be analysed using a frequency table.

8.7 Further analyses

- Vision related Quality of Life (VQoL) questionnaire at visit V09, V11 and V13.
- Visual acuity (ETDRS) on both eyes at visit V09 – V13
- Perimetry on both eyes at visit V09 – V13
- The ANTERION® from Heidelberg Engineering performed at V09 – V13
- Anterior eye segment measurement on both eyes at visit V09 – V13:
 - Optical coherence tomography (OCT), Central cornea thickness (CCT)
 - Slit-lamp biomicroscopy (Lids, Conjunctiva, Cornea, Anterior chamber, Iris Pupil, Lens, Anterior vitreous body)
 - Gonioscopy (angle open to (Shaffer), pigmentation of Trabecular meshwork)
- Posterior eye segment measurement:
 - Biomicroscopy (dilated, fundus) on both eyes at visit V09 – V13
 - Optical coherence tomography (OCT) on both eyes at visit V09 – V13

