### **Histology Findings**

Images of the in-situ situation and during explantation were taken by digital microscopy (Keyence 2000). The implantation sites did not reveal any gross lesion. The implants were visible through the overlaying tissue. In two samples (sample no. 2.2 and 4.2, right), there was distinct bubbles noted in the retina. Furthermore, on the inner eye surface, a striated tissue overlaying the implant was recorded in these samples. Histologically, these regions correlate to a partial replacement of a cyst-forming fibrotic reaction. They are deemed to represent remainders of a traumatic insult during surgery.

The histology examiner found the implant pouch (if visible on the section) to be located in all samples between choroidea and sclera. Further analysis did not reveal any indication of pathological changes in all samples.

 IOP Implantdata Ophthalmic Products GmbH	Clinical Investigation Plan ARGOS-SC01_Follow-up	Revision C  Page 34 of 97
---	---	---------------------------------

The implant was tolerated by the tissue fully. In some sample, even a fibrotic reaction was not traceable. In other samples, the fibrotic reaction consisted of an extremely thin rim of connective fibers. Only in two eyes, a few macrophages attached to the inner capsule surface were found. No other inflammatory reactions could be noted.

In three eyes, focally limited degeneration of the retina consisting of a partial replacement by a cyst-forming fibrotic reaction was noted by the histology examiner. By digital microscopy, it correlated to small bubbles and striations in the retina overlaying the implant. These findings were also assessed by the surgical team.

The surgeon performing all implantations reported difficulties forming a suprachoroidal cavity in rabbits, compared to the same task when performed in human eyes (surgeon has extensive experience in suprachoroidal implantation of Ologen implants of similar size). He presumed there are tissue adhesions between the rabbit sclera and choroidal, which he never experienced in human eyes. This is one likely explanation for the additional mechanical insult that have been reported by the histological examiner. Implantation in human eyes should be easier to perform, with significantly reduced mechanical irritation.

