#### **8.3.12.8 Visual Field (Perimetry)**

The purpose of visual field testing is to determine both the outer limits of visual perception by the peripheral retina and the varying qualities of vision within that area. Perimetry is performed to obtain an accurate examination of the peripheral extent of the visual field. Automated perimeters will be used either with standard glaucoma field, field 30-2 or equivalent. This should always be done on **both eyes** in order to compare study and fellow eye.

 Implantdata Ophthalmic Products GmbH	Clinical Investigation Plan ARGOS-SC01_Follow-up	Revision C  Page 61 of 97
---	---	---------------------------------

A change of the perimeter during the study should be avoided.

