#### **9.2 Sample Size Calculation**

Given by the exploratory nature of this study, the sample size is not driven by the need for a formal statistical hypothesis test with a certain degree of power. Instead, this study is driven by the desire to obtain a clinically meaningful amount of data to evaluate the long-term safety and performance of the ARGOS-SC system in patients who have been already implanted with the study device. Therefore the maximum sample size is 24. The minimal sample size for this study is at the Sponsor's direction. This is considered to be appropriate since no experimental treatments are planned and all assessments with exception of IOP measurement using the ARGOS-SC device are established standard methods.

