#### **9.3 Level of significance and the power of the clinical investigation**

Significance level is set to 0.10, Power to 80%.

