#### **9.8 Treatment of missing, unused and spurious data, including drop-outs and withdrawals**

All data of the patients will be used as available. All analyses will be performed on observed cases only. Missing data will not be replaced. Implausible values will be only excluded from the analysis if reasonable. The reason for exclusion will be given in the footer of the table or description of the figure. Patients terminating the trial prematurely due to whatever reason will be evaluated like any patient completing the trial as per protocol, within the analysis sets they qualify for.

Subjects who dropped out during a scheduled visit will be counted for that visit.

 Implantdata Ophthalmic Products GmbH	Clinical Investigation Plan ARGOS-SC01_Follow-up	Revision C  Page 72 of 97
---	---	---------------------------------

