3.3 Sample size calculation

Given by the exploratory nature of this study, the sample size is not driven by the need for a formal statistical hypothesis test with a certain degree of power. Instead, this study is driven by the desire to obtain a clinically meaningful amount of data to evaluate the long-term safety and performance of the ARGOS-SC system in patients who have been already implanted with the study device. Therefore, the maximum sample size is 24. The minimal sample size for this study is at the Sponsor's direction. This is considered to be appropriate since no experimental treatments are planned and all assessments with exception of IOP measurement using the ARGOS-SC device are established standard methods.

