8.1.2 Statistical outputs

8.1.2.1 Tables and graphics

Percentages will be based on the number of subjects in the analysis set.

Categorical variables will be summarized by the number of patients (n) and percentages (%). Percentages will be rounded to one decimal place.

In addition, for the primary endpoints (response rates) the 95% confidence intervals will be calculated.

Continuous variables will be summarized using descriptive statistics, including

- number of patients with non-missing data (n)
- arithmetic mean (Mean)
- 95% confidence interval of mean (if indicated)
- standard deviation (SD)
- median (Median)
- lower (25%, Q1) and upper (75%, Q3) quartile
- minimum (Min) and maximum (Max).

Analyses by visit will be performed irrespective of any time window deviations.

Some mock-up tables are presented in the appendix of this SAP.

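### Visual acuity and perimetry are planned with no within-eye change from V09 and no count of worsened eyes, so vision loss in a few of at most 24 implanted eyes would not be systematically identified or counted

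*SAP*

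**What the plan says.** **Planned analysis.** SAP 8.7 lists "Visual acuity (ETDRS) on both eyes at visit V09" through V13 and gives perimetry the same one-line entry. Neither entry names a statistic, a change score, a loss threshold or a perimetric parameter. SAP 11.3.1 allots one table per measure and eye (Tables 2.3.2–2.3.5). It lists no change or shift table, and none of the mock-ups in the text reviewed covers these four tables.

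**Default summary.** For continuous variables, SAP 8.1.2.1 gives n, mean, SD, median, quartiles, minimum and maximum, with a CI of the mean where indicated. Change from baseline is not among them.

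**What is collected.** V09 is the baseline visit (Protocol 8.3.9 and 8.3.15). Acuity is recorded as a letter count with the reading distance (Protocol 8.3.12.7). On perimetry, Protocol 8.3.12.8 says "This should always be done on" both eyes, so that the implanted eye can be set against its fellow, and it discourages changing perimeter. Protocol 9.1 asks for separate analysis of the two eyes to make such comparisons possible.

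**Sample and missing data.** On size, SAP 3.3 says: "Therefore, the maximum sample size is 24". On missing data, Protocol 9.8 says: "All analyses will be performed on observed cases only. Missing data will not be replaced".

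**Individual-level outputs.** Abnormal ophthalmic findings are listed by patient (SAP 8.1.2.2, Listing 3), and every adverse event is tabulated and listed (SAP 8.8.1). Lasting impairment of a body function counts as serious (Protocol 10.2.2).

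**The concern.** Long-term safety of a permanent implant is a secondary objective, and Protocol 8.1.2 states that safety events have no control group. Protocol 7.3 adds that the relation of ophthalmic events to the implant cannot be assessed independently. Each eye's own V09 value and the patient's fellow eye are therefore the best internal references, and the tables as specified use neither as a paired reference.

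Glaucoma patients can differ widely in acuity and field, and a per-visit group summary mixes that spread with any change. A drop in two or three eyes barely moves the centre of the distribution. Because visits are summarised on whoever attends, an eye that leaves the study also leaves the later summaries. Tables of this kind can be read as showing stable vision when some eyes have lost a good deal.

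The animal work gives a modest further reason to look. In the second rabbit study, "In three eyes, focally limited degeneration of the retina consisting of a partial replacement by a cyst-forming fibrotic reaction was noted". The protocol offers explanations specific to the rabbit eye, so this supports routine checking of visual function and no more.

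**Working it through.** **1. Is there a figure to reproduce?** No. Protocol 9.2 says "the sample size is not driven by the need for a formal statistical hypothesis test with a certain degree of power". The alpha and power in Protocol 9.3 have no effect size attached, and no document gives an SD or a loss threshold for acuity. What follows is an illustration.

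**2. Inputs.** n = 24 eyes (SAP 3.3). Assumed: between-eye SD of 10, 15 or 20 letters; mean 75 letters; SD of within-eye retest change 5 letters; losses of 15 or 30 letters in two or three eyes.

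**3. Shift of the visit mean** = (eyes × loss) / 24.
- 2 × 15 / 24 = 1.25 letters; 3 × 15 / 24 = 1.9
- 2 × 30 / 24 = 2.5 letters; 3 × 30 / 24 = 3.75

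**4. 95% CI half-width of a visit mean** = t(0.975, 23) × SD / √24, with t = 2.069.
- SD 10: 4.2 letters; SD 15: 6.3; SD 20: 8.4

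All four shifts lie inside the narrowest half-width. With an SD of change of 5 letters, the half-width for a mean *change* is 2.069 × 5 / √24 = 2.1 letters. That is tighter but still wider than 1.25 or 1.9, so a mean change alone is not enough and a count of eyes is needed too.

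**5. The other planned statistics.** 20,000 simulated data sets per scenario, on the inputs above, with scores held between 0 and 100. Entries separated by slashes are for SD 10 / 15 / 20.

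| Eyes × letters lost | V13 mean below V09 CI | Minimum falls ≥10 letters | Mean number of eyes with observed loss ≥15 |
|---|---|---|---|
| 2 × 15 | 1 / 0 / 0% | 24 / 18 / 15% | 1.0 |
| 3 × 15 | 2 / 0 / 0% | 33 / 25 / 20% | 1.5 |
| 2 × 30 | 8 / 0 / 0% | 76 / 52 / 39% | 2.0 |
| 3 × 30 | 37 / 4 / 0% | 86 / 65 / 50% | 3.0 |

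With no true loss, the minimum falls by 10 letters or more in 3% of data sets. For three 30-letter losses the median moves by about 2.0 / 2.7 / 3.2 letters. The minimum therefore signals large losses some or most of the time and 15-letter losses seldom. It never says how many eyes are affected.

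**6. What a count would show.** Exact (Clopper–Pearson) 95% limits for x of 24, from Beta(0.025; x, 25 − x) to Beta(0.975; x + 1, 24 − x):
- 0/24: 0% (0–14.2%)
- 1/24: 4.2% (0.1–21.1%)
- 2/24: 8.3% (1.0–27.0%)
- 3/24: 12.5% (2.7–32.4%)

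These describe *observed* losses at or beyond the threshold. The last column of the table shows the limit: a true loss lying exactly on a 15-letter threshold is counted only about half the time, because of retest noise. A 30-letter loss is counted almost always. This argues for a second, lower threshold and a patient listing beside the count.

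**7. Observed cases.** Suppose all 24 eyes average 75 letters and one 75-letter eye falls by 30. If it attends, the mean is 75 − 30/24 = 73.75. If it does not, the other 23 still average 75 and the table shows no change.

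**The case against.** The strongest reply is that the plan has several routes to individual cases. The minimum is a planned statistic, and step 5 shows that it often moves when losses are large. Abnormal findings are listed by patient, and nothing excludes acuity or field from that listing. Investigators examine patients and ask about new problems at every visit (Protocol 8.3.10 and 10.3), all adverse events are listed, and lasting functional loss is serious by definition. All of this stands. A reader might infer from the table plan that vision loss would be invisible; the documents do not support that. What they lack is a trigger: abnormal is undefined for acuity and field, adverse event reporting rests on the investigator's judgement, and Protocol 7.3 names only temporary visual impairment among the events of interest.

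A reader might also infer that the SAP contradicts the protocol on the fellow eye. It does not. Protocol 9.1 prescribes separate analysis, and the SAP follows it. A paired contrast is a better use of the same data, not a missed obligation.

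SAP 8.7 names no statistic, so the cross-sectional reading rests on SAP 8.1.2.1 and the table titles. That is fair, but nothing there would lead a programmer to produce a change score.

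The rabbit finding is weak support. The protocol attributes it to surgical trauma, reduced retinal nourishment and relative implant size, and places the human implant largely away from central retina (Protocol 4.7.2.1).

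Dropout bias is possible, not shown. Protocol 8.3.2.2 keeps data up to withdrawal and seeks end-of-study assessments from early discontinuers who permit it.

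Finally, acuity and perimetry are further analyses in an exploratory, descriptive study. That limits the weight of the point, but safety is a stated objective and the remedy is cheap.

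**Conclusion.** The point holds in this form: for visual acuity and perimetry the plan contains no within-eye change from V09 and no count of worsened eyes. Loss in a few implanted eyes would therefore be neither systematically identified nor counted. Detection would depend on the visit minimum, an abnormal-findings listing without an acuity or field definition, and investigator reporting.

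On assumed SDs of 10–15 letters, two or three 15-letter losses move the visit mean by 1.25–1.9 letters against a half-width of 4.2–6.3. A count would report the same observed losses as 8.3% or 12.5% of eyes.

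The SDs, mean, retest noise and letter thresholds are assumptions; only the cap of 24 comes from the documents. With fewer eyes each loss shifts the mean more, but the interval widens too. The absence of change scores and loss counts does not depend on any of these assumptions. Some pages, including the listing mock-up in SAP 11.4.2, were not in the text reviewed; the conclusion rests on SAP 8.7, 8.1.2.1 and the lists of tables and listings.

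It would go too far to conclude that the implant harms vision, or that a loss count could establish cause. The design cannot settle that, and even zero losses in 24 eyes leaves an upper limit of 14.2%.

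**What to change.** Amend SAP 8.7 and Tables 2.3.2–2.3.5 before database lock:

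- Report within-eye change from V09 at V10–V13 and at the last available visit, including early discontinuers. Do this for ETDRS letters and for one named perimetric global index, computed only within the same perimeter.
- Report the number of eyes exceeding a pre-specified loss threshold, with an exact 95% CI and a stated denominator. Thresholds of ≥10 and ≥15 letters are examples; the sponsor should justify the choice, allowing for retest variability.
- Report the paired study-minus-fellow difference in change, descriptively.
- Add a patient-level listing of acuity and perimetry by visit for both eyes.

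The cost is SAP wording, extra table rows and one listing. No patients, visits or measurements are added, and the sample size is unaffected. The safety results may look slightly less favourable than the per-visit summaries would.

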8.8 Further safety analyses

8.8.1 Adverse events

All safety analyses will be conducted on the FAS set.

The AE terms will be coded according MedDRA into System Organ Class (SOC) and Preferred Terms (PT) of *Implandata Ophthalmic Products*.

Number of adverse events as well as the number and relative frequency of patients reporting adverse events will be tabulated by System Organ Class and Preferred terms.

The incidences of AEs will be stratified by:

- Seriousness
- Severity
- Relationship to medical device
- Expectedness
- Action taken
- Outcome
- Criterion to classify as serious

The incidence of AEs will be summarized to include only one occurrence of an AE class per patient. If a patient has multiple AEs of the same class, then that term will only be counted once. All AEs will be listed.

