#### 8.1.2 Description of the measures to be taken to minimize or avoid bias

All eligible patients will be enrolled.

There will be no control group for safety events. Incidence, nature and severity will be compared to literature of standalone NPGS. To allow assessment of performance, measurements of IOP with the ARGOS-SC sensor will be compared to those obtained with the standard GAT method and Pascal DCT at the same time point. To prevent possible influence of prior knowledge of the IOP value obtained with the ARGOS-SC, which is objectively displayed, measurements will always be made first with GAT/DCT. Data on all device deficiencies will be recorded.

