## 9. STATISTICS

### 9.1 Statistical design, method and analytical procedures

The primary purpose of this investigation is to assess the long-term performance of the investigational device. In order to investigate the long-term performance of the investigational device, the data obtained from the study will be evaluated with explorative and descriptive analysis of the outcome variables described below. Generally, summary tables will be presented. These are either frequency tables (ordinal or nominal data) or summary statistics with mean, standard deviation, median, minimum, maximum, lower and upper quartile (metric data).

Outcome variables that are recorded separately for the study eye, i.e. the eye with implanted ARGOS-SC sensor, and the fellow eye, i.e. the eye without ARGOS-SC sensor, will be also analyzed separately to allow comparisons between the study and fellow eyes.

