### **10.3 Recording of Adverse Events (AEs)**

All AEs will be documented throughout the clinical trial as per ISO 14155, chap. 7.4.1, meaning from the point of inclusion/signing of the informed consent, until resolution or stabilization, or for a maximum of 7 days after the last subject has been discharged from the study.

All AEs will be reported on an Adverse Event Form, one for each Adverse Event, which is part of the CRF.

AEs will be collected with a non-leading question at each visit: "Have you had any new or worsening health problems since the last visit?" as well as by reporting those events directly observed and spontaneously reported by the subject. Clearly related signs, symptoms and abnormal diagnostic procedures should preferably be grouped together and recorded as a single diagnosis or syndrome whenever possible. Seriousness, severity (mild, moderate or severe), outcome and relationship to investigational device as well as expectedness and action taken will be recorded in the AE page of the CRF. Start and end date and time of the event will also be recorded. SAEs will be followed until resolution or stabilization. AEs will be followed until resolution or stabilization, or for a maximum of 7 days after the last subject has been discharged from the study.

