8.8.3 Medication

Coding of concomitant medication by ingredients will be conducted of *Implandata Ophthalmic Products*.

Concomitant medication during the Follow-up Phase (V09 until V13) will be shown as follows:

- Concomitant glaucoma medication of the study eye in total (N,%) and stratified by ingredients (N,%)
- Concomitant glaucoma medication other than study eye in total (N,%) and stratified by ingredients (N,%)
- Concomitant medication other indication than glaucoma in total (N,%) and stratified by ingredients (N,%)

The details regarding application forms, dosages, specified medications will be listed only.

9 Changes to Planned Analysis from Study Protocol

ARGOS-SC self-measurements were not recorded

Interim analyses are not performed according Note to File of 29.08.2022

10 References

1. ICH Topic E3: Structure and Content of Clinical Study Reports (CPMP/ICH/137/95 – July 1996).
2. ICH Topic E9: Statistical Principles for Clinical Trials (CPMP/ICH/363/96 – September 1998).
3. ARGOS-SC01_Follow-up (Clinical Investigation Plan), Rev. C, 27.05.2021.
4. Lawrence I-Kuei Lin (March 1989). "A concordance correlation coefficient to evaluate reproducibility". *Biometrics*. 45 (1): 255–268

11 Appendix

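### Adverse-event tables do not separate study eye from fellow eye, so ocular AE incidence is an any-eye figure and not the implanted-eye incidence needed for the NPGS literature comparison

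*SAP*

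**What the plan says.** **AE tabulation.** Under SAP 8.8.1, the number of events and the number and relative frequency of "patients reporting adverse events will be tabulated by System Organ Class and Preferred terms". The section continues "The incidences of AEs will be stratified by" and names seven factors: seriousness, severity, relationship to the device, expectedness, action taken, outcome and the criterion for seriousness. The counting rule is "If a patient has multiple AEs of the same class, then that term will only be counted once". It also says "All AEs will be listed".

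**AE recording.** Protocol 10.3: "Seriousness, severity (mild, moderate or severe), outcome and relationship to investigational device as well as expectedness and action taken will be recorded" on the AE page of the CRF, together with start and end dates. The affected eye is not mentioned there.

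**Safety benchmark.** Protocol 8.1.2: "There will be no control group for safety events. Incidence, nature and severity will be compared to literature of standalone NPGS". Protocol 7.3 repeats the comparison, lists AEs of particular interest, and says that the relationship of ophthalmic AEs to the implant cannot be independently assessed.

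**Treatment of the two eyes elsewhere.** Under Protocol 9.1, outcome variables recorded separately by eye "will be also analyzed separately to allow comparisons between the study and fellow eyes". In the SAP table list (11.3.1), Tables 2.3.2–2.3.11 come in study-eye and fellow-eye pairs for acuity, perimetry, ANTERION, anterior segment and posterior segment. SAP 8.8.3 reports "Concomitant glaucoma medication of the study eye in total" and, separately, glaucoma medication other than in the study eye.

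**The concern.** The assessment schedule has acuity, perimetry, slit lamp, gonioscopy, funduscopy and OCT done on both eyes at every visit from V09 to V13. Ocular events in the non-implanted eye can therefore be found and reported. In the planned tables such an event adds to the same preferred-term row, and to the same patient percentage, as an event in the implanted eye.

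This matters because the study has one arm and the protocol relies on outside literature to put its AE incidence in context. Literature on standalone NPGS describes what follows surgery on an eye. The matching quantity here is the incidence in the eye that had surgery and carries the sensor. A table that mixes eyes can only equal or exceed that quantity, and the reader cannot tell by how much. Nor could the reader see from these tables whether events cluster in the implanted eye.

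**Working it through.** **Step 1: is there an eye dimension anywhere in the AE outputs?**

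| Place | Eye shown? |
|---|---|
| SAP 8.8.1, seven stratifiers | No |
| SAP 11.3.1, titles of Tables 3.1.1–3.2.4 | No |
| SAP 11.4.1, mock-up 3.1.1 (SOC, PT, number of AEs, number of patients, %) | No |
| SAP 11.4.1, mock-up 3.2.1 (AE characteristics) | No |
| SAP 11.3.3, Listings 6–7 | Columns not shown in the text available |
| SAP 11.3.1, Tables 2.3.2–2.3.11 (examinations) | Yes |
| SAP 8.8.3 (glaucoma medication) | Yes |

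The plan splits by eye for examinations and for glaucoma medication, but not for AEs.

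**Step 2: what does the planned percentage estimate?** Let ps be the proportion of patients with a given ocular term in the study eye and pf the proportion with it in the fellow eye. A patient counts once if either eye is affected, so

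any-eye incidence = ps + (proportion with the event in the fellow eye only).

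A bilateral event does no harm to this percentage. The excess comes entirely from patients affected in the fellow eye alone. If the eyes are independent, the excess is (1 − ps) × pf, and any-eye incidence = 1 − (1 − ps)(1 − pf). Whatever the correlation, it lies between max(ps, pf) and min(1, ps + pf).

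**Step 3: size.** The documents give no AE rate or literature benchmark, so there is no planned figure to reproduce. The rates below are assumptions. N = 24 is the maximum in Protocol 8.3.6.

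| ps | pf | Independent eyes | Range over any correlation | Expected patients, any eye (study eye alone) |
|---|---|---|---|---|
| 10% | 0% | 10% | 10% | 2.4 (2.4) |
| 10% | 2% | 1 − 0.90 × 0.98 = 11.8% | 10–12% | 2.8 (2.4) |
| 10% | 5% | 1 − 0.90 × 0.95 = 14.5% | 10–15% | 3.5 (2.4) |
| 10% | 10% | 1 − 0.90 × 0.90 = 19.0% | 10–20% | 4.6 (2.4) |
| 20% | 10% | 1 − 0.80 × 0.90 = 28.0% | 20–30% | 6.7 (4.8) |

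**Step 4: what is hidden.** Suppose five patients have a term in the study eye only and a sixth has it in the fellow eye only. The table shows 6/24 = 25.0%. The study-eye figure is 5/24 = 20.8%, exact 95% interval 7.1% to 42.2%. The split of five to one appears in no AE table.

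**The case against.** Much can be said for the plan as written.

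- **Protocol 9.1.3 itself prescribes patient-level SOC and PT tables without an eye split.** SAP 8.8.1 follows it. A reader might infer that the SAP breaks Protocol 9.1, but that rule covers only variables recorded separately by eye, and the documents do not show whether AEs are. This stands: the SAP is out of line with its own by-eye approach elsewhere, but no breach of the protocol is shown.
- **Systemic events.** A reader might infer that systemic and ocular events are pooled too. They have their own SOC and PT rows and meet only in the grand total, which is not the figure for comparing named ocular AEs.
- **Fellow eye as control.** A reader might infer that a built-in control has been thrown away. Protocol 8.1.2 plans no control group for safety events. The sensor was implanted during surgery on the same eye (Protocol 8.2.1), so a contrast between eyes confounds implant with surgery. By-eye examination tables are kept.
- **Some AEs of interest belong to the operated eye by nature**, such as perforation of the trabeculo-Descemet's membrane. For these there is no distortion. Others on the list, such as retinal detachment, hyphema or anterior chamber inflammation, can occur in either eye.
- **Device-related tables (3.1.3, 3.1.4, 3.2.3, 3.2.4) and full listings exist.** The tables help in part. They rest on a causality judgement that Protocol 7.3 says cannot be independently assessed, and a device-related subset is not like-for-like with literature on surgery without a device. The listings help only if they show the eye.
- **The AE form may already record the eye.** It is not among the documents, so Protocol 10.3 cannot be read as proof that laterality is uncollected.
- **Precision.** With at most 24 patients, intervals are wider than the shift. That is true, but imprecision is no reason to report a different quantity.

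**Conclusion.** The point holds as a reporting defect. The AE outputs give an any-eye patient incidence for ocular terms, while the protocol's own benchmark calls for the implanted-eye incidence. The device-related tables do not close the gap.

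The size cannot be settled from the documents. At an assumed study-eye incidence of 10% the excess runs from nothing, if no fellow-eye events occur, to 9.0 percentage points at an equal fellow-eye rate with independent eyes. A reader might infer that reported incidence will be almost double. That needs equal rates and independence; a lower fellow-eye rate or positive correlation between the eyes shrinks it, and no AE rate in the documents supports it.

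The study is exploratory and descriptive, so no test or decision rule is affected. The change is worth making because it is cheap and gives the plan the quantity it says it wants. A neighbouring gap should be closed with it: the SAP does not say how the literature comparison will be carried out.

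**What to change.** In SAP 8.8.1:

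1. Classify every AE as study eye, fellow eye, both eyes or non-ocular. Take this from the AE form if it records the eye, otherwise from source documents.
2. Add these columns to Tables 3.1.1–3.1.4, and show the eye in Listings 6–7. A bilateral event counts in both the study-eye and the fellow-eye incidence.
3. State that the comparison with standalone NPGS literature uses study-eye ocular events only, in particular the AEs of interest in Protocol 7.3.
4. Show fellow-eye incidence beside it as description, with a note that it is not a control because the study eye also had surgery.
5. Record the split in SAP section 9 as an addition to the tables in Protocol 9.1.3.

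The SAP is to be finalised before database lock, and the classification should be fixed by then. The cost is coding work for at most 24 patients and smaller cells. No visits, patients or examinations are added.
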